Rationale	
In an effort to establish clinical evidence, this prospective, randomized clinical trial will assess and compare the efficacy of two different post-extraction bone grafting applications, Bone Allograft and Bone Allograft/Amnion, in 20 eligible adult subjects.
 
The study will assess the efficacy of each application to aid socket healing and preserve alveolar ridge integrity prior to full reconstruction with root-form endosseous dental implants.
 
The amniotic allograft is a cryopreserved allograft tissue matrix derived from human placental tissues recovered from live healthy donors. Amniotic tissue is an abundant source of collagen that provides an extracellular matrix to act as a natural scaffold for cellular attachment in the body. Collagen provides a structural tissue matrix that facilitates cellular migration and proliferation in vivo. The product was developed using a proprietary technique that morselizes the amnion in an effort to preserve its osteogenic properties in an injectable form. The “micro-scaffold” created by the morselized tissue matrix includes the residual proteins, growth factors, chemical compounds and cells naturally present in the placental tissues. The amniotic allograft growth factors are thought to enhance formation of a supportive scaffold for regeneration, to facilitate interactions between cell types, and to influence anti-inflammatory, anti-microbial and immunoprivilege activity.
 
Follow-up evaluations will assess osseous and soft-tissue healing at 1, 2, 4, and 7 weeks. Cone-Beam CT scans will be obtained immediately post-grafting and after 7 weeks.
 
At 8 weeks, a biopsy will be harvested from one site per subject and implants will be surgically positioned into the regenerated extraction sockets. Torque measurements at implantation will be recorded.
 
Implants will be uncovered 4-6 months post-implantation and subjects will be referred for permanent prosthetic attachment.
 
The study will evaluate the longitudinal outcome of early reconstruction with dental implants via two annual post-implant follow-up evaluations to be completed at 12 and 24 months following permanent prosthetic attachment.
 
Standardized, intra-oral periapical radiographic images will be obtained pre-surgery, immediate post-implant insertion, 7 weeks following implantation, when implants are uncovered, at permanent restoration, and at each follow-up evaluation.
 
Clinical photographs will be taken at each clinical visit or at investigator discretion.

Objectives	
To evaluate and compare post-treatment healing of hard and soft tissues in maxillary or mandibular aesthetic zones following procedures utilizing test and control grafting materials.
 
To evaluate longitudinal clinical outcome of dental implants surgically inserted into regenerated bone 8 weeks after tooth extraction and grafting.

Null	The following null hypothesis will be tested: there is no difference in post-extraction healing patterns between extraction sockets grafted with Bone Allograft (BA) and extraction sockets grafted

Hypotheses	with Bone Allograft + Amnion Allograft.
Randomization	
Participants will be stratified for smoking status and randomized to one of two treatment groups:
 
Test Group-1: Atraumatic extractions followed by Bone Allograft (BA) and collagen plug
 
Test Group-2: Atraumatic extractions followed by Bone Allograft/Amnion Allograft (AA) and collagen plug

Procedures	
Only treatment of non-adjacent sites will be included in the database. Each participant may have up to four non-adjacent sites selected for inclusion as study treatment sites.
 
Extractions Atraumatic extractions and graft procedures following the randomization table and standardized surgical procedures.
 
Three-dimensional images, acquired through Cone Beam Computed Technology (CBCT), will be captured immediately post-grafting. Prophylactic antibiotics will be dispensed, prescriptions for post-surgery antibiotics and analgesics (prn) will be written. Antibacterial mouth wash will be dispensed; written and verbal patient home-care instructions will be provided.
 
To preserve anterior aesthetics, during the healing phase, an Essix retainer will be made for each participant and inserted immediately after the extractions/grafting procedures.
 
Follow-up evaluations Performed at week-1, week-2, week-4, and week 7 will include:
 
 Assessment of post-surgical healing Assessment of adverse experiences Measurement of clinical parameters Clinical photographs Suture removal at week 2 A CBCT scan will be completed at week-7 
Biopsy and Implant Placement A biopsy, and surgical placement of implants completed at week-8
 
 Prophylactic antibiotics dispensed Pre-surgical oral rinse One bone-fill biopsy per patient, harvested by trephine (placed in fixative for later histological analysis) Measurement of clinical parameters Clinical photographs Surgeon's subjective observation of osseous fill quality (D-1-D-4). Measurements of torque at implantation will be recorded Immediate post-surgical intra-oral radiographs Prescriptions for post-surgery antibiotics and analgesics (prn) Antibacterial mouth wash and ice-packs dispensed Written and verbal home-care instructions 
Post-Insertion Follow-up Implant surgical follow-up assessment and suture removal will be performed after two-weeks.

	
Implants Exposed Mandibular implants will be exposed after approximately 4 months; maxillary implants will be uncovered after approximately 6 months.
 
Implant Restoration Implants will be restored in the conventional manner with aesthetically pleasing cemented single crown restorations by one of the investigators. Photographs and radiographs will be obtained at permanent restoration.
 
Longitudinal Follow-up Two annual follow-up evaluations will be completed at 12 months and 24 months from the date the permanent restoration is attached to the implant. Each assessment will include:
 
 Standardized intra-oral periapical dental radiographs Clinical photographs Measurement of clinical parameters Assessment of soft-tissue contours Assessment of overall aesthetics Assessment of implant/restoration interface
Population	
Twenty healthy adult patients (10 per group) of any ethnicity or gender whose treatment plan includes extraction of mandibular and/or maxillary pre-molars and/or maxillary anterior teeth and their replacement with root-form dental implants and who meet the entrance eligibility criteria will be consecutively recruited for enrollment in the study. See inclusion/exclusion criteria – Table 1.

Outcomes	
Histology and histomorphometric analyses (site biopsies)
 
Soft-Tissue aesthetic assessments (Jemp Indices and photographs)
 
Soft Tissue Health (PI & GI, and photographs)
 
Bone Support to Implants (standardized PA radiographs and image analysis)
 
Radiographic image analysis of osseous architecture changes at study sites over time

Statistical Analyses Plan	
Two-tailed t tests will be used to compare clinical characteristics between the test and control therapies for continuous variables with a normal distribution. Nonparametric (Wilcoxon) tests will be used otherwise.
 
For categorical variables, inter-group comparisons will be conducted using chi-square tests or Fisher's Exact Test, as deemed necessary.
 
To determine whether the groups experienced equivalent changes in bone growth from baseline to follow-up, paired t (or Wilcoxon signed-rank) and McNemar's tests will be used for continuous and categorical variables, respectively. The α level will be set at 0.05.
 
Statistical analysis will be carried out using SAS software version 9.2 (SAS Institute, Inc, Cary, North Carolina).

[figure not shown]

Table of Contents

1.0 BACKGROUND AND SIGNIFICANCE

1.1 Tooth Extraction Socket Preservation

Tooth extraction is often associated with resorption of alveolar ridge height and width and with compromised soft tissue contours.¹⁻⁸ An increasingly common periodontal practice combines skilled surgical technique with extraction site grafting. These procedures are thought to retard resorption of the socket volume while lending some control over bone-fill – thereby preserving the integrity of the alveolar ridge for future reconstruction with dental implants.

1.2 Amniotic Allograft

The study will assess the efficacy of amniotic allographs used to graft extraction sockets prior to reconstruction with dental implants. The amniotic allograft is a cryopreserved allograft derived from the placental tissues recovered from live healthy donors.⁹ It has demonstrated osteogenic properties in both animal studies and clinical applications.

Amniotic fluid has been shown to contain multipotential cells that can differentiate into all three germ layers of the human body, including osteoblasts that can subsequently initiate bone formation with the deposition of osteoid. A plethora of growth factors such as Epidermal Growth Factor (EGF), Transforming Growth Factor beta (TGF- β), Fibroblast Growth Factor (FGF), Platelet Derived Growth Factor A&B (PDGF A&B) are associated with amniotic tissue and fluid. All these growth factors interact with different cell lines through their transmembrane receptors and may act to accelerate not only bone formation but also soft tissue healing. The product was developed using a proprietary technique that morselizes the amnion in an effort to preserve its osteogenic properties in an injectable form. The “micro-scaffold” created by the morselized tissue matrix includes the residual proteins, growth factors, chemical compounds and cells naturally present in the placental tissues. The amniotic allograft also contains a series of extracellular proteins such as fibronectin, laminins, vitronectin and cytokines as well as collagen that create a supportive scaffold that facilitates the communication and interaction amongst cells.¹⁰

In addition to this, amniotic tissue and fluid is characterized by anti-inflammatory,¹⁰ anti-microbial¹¹ and immunoprivileged actions.^{12,13,14} Anti-inflammatory activity is expressed by the suppression of the pro-inflammatory cytokines such as interleukin-1 α and interleukin-1 β as well as by the inhibitors of metalloproteases that are secreted from polymorphonuclear cells and macrophages. Anti-microbial property is evident with the presence and release of β -defensins, a group of antimicrobial peptides. The immunoprivileged action is associated with the expression Human Leukocyte Antigens, HLA-G that eliminates the acute rejection by serving as a ligand for the inhibitory receptors of the natural killer cells and the macrophages. Moreover, there is no expression of HLA-A, -B, -D, and -DR antigens on the cell surface of the amniotic embryonic cells and consequently there is no immune response.

Lastly, amniotic tissue and fluid has angiogenic ability that is demonstrated by the secretion of angiogenic factors by the amniotic epithelial and stromal cells. Vascular Endothelial Growth Factor (VEGF), Interleukin-8 (IL-8), Angiogenin, Interferon- γ , Interleukin-6 (IL-6), basic Fibroblast Growth Factor (bFGF), Epidermal Growth Factor (EGF) and Platelet-Derived Growth Factor (PDGF) are produced. However the amniotic epithelial cells express some anti-angiogenic factors that they may affect to some degree the net angiogenic potential of the amniotic allograft.¹⁵

1.3 Reconstruction with Dental Implants

Dental implants have been used in dentistry for decades in an attempt to reestablish function and aesthetics to areas of the mouth where natural dentition is lost.^{16, 17} Materials and designs of dental implants^{18, 19, 20} have evolved over the years to arrive at the optimal combination of materials, shape and surface texture that would induce permanence to the restoration.

1.4 A Rigorous Test

In an effort to establish further clinical evidence, the current study will assess and compare the efficacy between two randomly assigned different bone grafting applications in non-adjacent aesthetic zone extraction sockets. Placing implants into augmented bone represents the most rigorous test of potential bone-preserving therapies.

2.0 INVESTIGATIONAL DESIGN

2.1 Purpose

The purpose of this prospective, randomized clinical trial is to compare healing of extraction sockets treated with Bone Allograft and sockets treated with Amnion-enhanced Allograft. The study will also compare the efficacy of early reconstruction with dental implants placed into the regenerated bone.

2.2 Objectives of the Investigation

The overall objective of this investigation is two-fold:

1. To evaluate outcomes with respect to osseous and soft tissue healing of grafted extraction sockets between Bone Allograft (control therapy) and Bone Allograft/Amniotic allograft (test therapy).
2. To evaluate longitudinal stability of dental implants after placement into grafted extraction sockets.

2.3 Hypotheses and Specific Aims

The trial will test two hypotheses:

Hypothesis-1: Grafting with Bone Allograft is an efficacious method of enhancing the development of new bone fill in extraction sockets.

Hypothesis-2: Bone Allograft/Amniotic allograft will aid osseous healing and will preserve alveolar ridge dimensions of extraction sockets more effectively than extraction sites grafted with Bone Allograft alone.

Specific Aims

- 1: Compare the efficacy of bone grafting with and without enrichment with amnion.
- 2: Compare alveolar ridge dimensions between groups after 7 weeks of post-extraction healing.
- 3: Compare soft tissue healing between groups at week-1, week-2, week-4 and after 7 weeks of post-extraction healing.

- 4: Assess quantitative bone fill between groups after 7 weeks of post-extraction healing
- 5: Compare qualitative bone fill between groups after 7 weeks of post-extraction healing.
- 6: Assess and compare the relationship of osseous healing and implant stability at insertion across groups after 8 weeks of post-extraction healing.
- 7: Compare implant stability between groups at 12 months and 24 months post-restoration.
- 8: Assess changes in longitudinal crestal bone level between groups at 12 and 24 months after permanent prosthetic attachment.

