3.0 STUDY POPULATION

3.1 Entrance Criteria

Twenty healthy adult patients (10 in each group) of any ethnicity or gender whose treatment plan includes extraction of maxillary anterior teeth and/or mandibular and/or maxillary pre-molars and their replacement with root-form dental implants will be consecutively recruited for enrollment in the study.

Participants must be at least 19 years old with demonstrated ability to understand the proposed treatment recommendations and prognosis and be able to provide informed consent, in English, without the aid of ad-hoc translation from another language. Decisionally-impaired adults and/or minors, who cannot consent for themselves, will not be enrolled; women who are pregnant or lactating at the time of enrollment will not be included. Women will be tested for current pregnancy status.

Prior to enrollment, prospective participants must agree to be available for the entire duration of the study, be compliant with needed study-related evaluations and demonstrate a willingness to comply with strict time-line requirements. Certain health and medication exclusions apply (table 1).

Table 1 Entrance Criteria

Inclusion	Exclusion
Existence of one or more non-adjacent teeth in the aesthetic zone that are scheduled for extraction	Pregnancy or lactating at the time of enrollment
Healthy enough to undergo the proposed therapy without compromise to their existing health status	Previous malignant neoplasm
Demonstrated willingness to comply fully with protocol time-line and procedural requirements	A known hypersensitivity to DBM
At least nineteen years old	A known hypersensitivity to Titanium metal
Able to read and understand written English without the aid of ad hoc interpretation	Any health condition that in the opinion of the clinical investigators may adversely affect bone healing
Able to cognitively understand the proposed study therapy and possible prognosis	Any medication that in the opinion of the clinical investigators may adversely affect bone healing
Able to consent for their own inclusion in the study	Any indication of an inability to make autonomous decisions

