4.0 SUMMARY OF STUDY PROCEDURES

4.1 Enrollment and Treatment Planning

After completing an individualized, private consent discussion and obtaining informed consent, a pre-surgical assessment will be completed. Each enrolled participant will be seen for an initial evaluation to include assessments of medical and dental conditions that will verify compliance with entrance criteria and for collection of demographic data.

Participants will be assigned a unique identification number. Information will be recorded on baseline case report forms (CRFs) developed specifically for this study.

Each participant may have up to four non-adjacent sites selected for inclusion as study treatment sites. Through consultations with prosthodontic clinicians, the documented treatment plan will be reviewed and revised if necessary to develop a therapy that will be of most benefit to the participant.

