4.2 Randomization

Participants will be stratified for smoking status and randomized to one of two extraction/grafting groups. In the case of multiple tooth sites within one participant, all the tooth sites will be assigned to receive the same graft material.

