4.3 Randomized Groups

Control Group 1: Atraumatic extractions followed by grafting with Bone Allograft mixed with sterile saline and collagen plug.

Test Group 2: Atraumatic extractions followed by grafting with Bone Allograft mixed with Amnion graft and collagen plug.

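### Section 2.3 says the trial will test whether bone allograft enhances new bone fill, but every study socket receives bone allograft and no comparator or benchmark is given

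*Combined protocol and SAP*

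**What the plan says.** Section 2.3 opens with "The trial will test two hypotheses". The first is "Hypothesis-1: Grafting with Bone Allograft is an efficacious method of enhancing the development of new bone fill in extraction sockets". The second is that adding amnion to the allograft does better than the allograft alone.

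Section 4.3 defines the only two groups: "Control Group 1: Atraumatic extractions followed by grafting with Bone Allograft mixed with sterile saline and collagen plug" and "Test Group 2: Atraumatic extractions followed by grafting with Bone Allograft mixed with Amnion graft and collagen plug". Section 4.6 applies the assigned material to each socket in each group. Section 4.2 adds that, where a participant has several sites, "all the tooth sites will be assigned to receive the same graft material".

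The synopsis states one null hypothesis. It is that "there is no difference in post-extraction healing patterns between extraction sockets grafted with Bone Allograft (BA) and extraction sockets grafted" with bone allograft plus amnion. It contains no null for Hypothesis-1.

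The measurements that bear on bone fill are these:

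- a CBCT scan immediately after grafting and another at week 7 (5.0);
- one biopsy per participant at week 8, read for new bone, residual graft and soft tissue (13.1);
- paired tests of change from baseline to follow-up (13.4).

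**The concern.** To say that a graft enhances new bone is to compare it with healing without that graft. A trial in which both arms share the graft can show what amnion adds to it, but not what the graft itself does. The protocol nevertheless says that the second question will be tested.

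At stake is the final report. It must either leave a stated hypothesis unanswered or answer it with a level or a change in one arm that has nothing to be compared with. Two other sentences make the second course easier. The synopsis Rationale promises to assess how efficacious each application is in aiding socket healing. Section 11.1 says histology will bear on the success or failure of the graft materials in promoting new bone, although there the claim is qualified as relative.

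**Working it through.** The plan attaches no sample size, effect size, threshold or benchmark to Hypothesis-1, so there is no figure of its own to reproduce. The check is whether any planned comparison contains the effect of bone allograft.

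**1. Count of ungrafted sites.** Inputs: "Twenty healthy adult patients (10 in each group"), from 3.1; at least one qualifying tooth, from Table 1; and "Each participant may have up to four non-adjacent sites selected for inclusion as study treatment sites", from 4.1. Possible study sites run from 20 × 1 = 20 to 20 × 4 = 80. By 4.3 and 4.6 all are grafted with material containing bone allograft, so ungrafted study sites = 0. By 4.2 there is no within-mouth contrast either.

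**2. Between-arm comparison.** Let m be mean healing with the common procedures but no allograft, b the effect of bone allograft, and a the additional effect of amnion.

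- Control arm mean: m + b
- Test arm mean: m + b + a
- Difference: (m + b + a) − (m + b) = a

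The term b cancels whatever its size and whatever the sample size. A simulation of the planned t test (10 v 10, two-sided 0.05, 20,000 replicates, a = 0) agrees. With b set at 0, 1 and 3 SD, the test rejects in 4.7%, 5.2% and 5.0% of runs, which is its nominal level each time.

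**3. Paired change within the allograft arm (13.4).** The mean change combines spontaneous healing and any graft effect. One observed mean cannot separate two unknowns. To illustrate, take zero graft effect and an assumed natural change of d SD, with n = 10, 9 degrees of freedom and noncentrality d√10:

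| Assumed d | d√10 | Probability that the paired t test is significant |
|---|---|---|
| 0.25 | 0.79 | 10.9% |
| 0.5 | 1.58 | 29.3% |
| 1.0 | 3.16 | 80.3% |
| 1.5 | 4.74 | 98.7% |

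The documents give no SD or expected change, so the values of d are assumptions. They show only that a significant paired test would not be evidence for the graft. In addition, the baseline scan follows packing of the socket to complete fill (4.6, 5.0). The change is therefore not growth from an empty socket, and nothing in the documents says that CBCT separates new bone from packed graft.

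**4. Week-8 histology (13.1).** This does separate new bone from residual graft. It is taken once, so it has no baseline. It gives the level m + b in the allograft arm and m + b + a in the other, and 13.1 compares the two grafted groups with each other.

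**5. Other possible references.**

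- The reference list (17.0, item 8) includes a human study of allograft plus a membrane against extraction alone. Section 1.1 cites it only within a group reference on resorption, and no value is taken from it.
- The graft success criterion in 11.1 is the absence of allergy, toxic reaction and gross infection. It sets no bone-fill threshold.
- Section 13.1 uses the term *natural bone fill*. The documents seen do not define it, and no ungrafted study site exists to which it could refer.

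**The case against.** The best reply is that this is one stray sentence. The synopsis null, the purpose in 2.1 and all eight Specific Aims compare the two grafted groups. Hypothesis-1 has no endpoint, threshold or sample size of its own. Deleting it would change no planned between-arm test. All of this is correct, and it limits the consequence. It does not remove the contradiction, because 2.3 says in terms that the hypothesis will be tested.

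A second reply is that the question could be answered from outside, by a one-sample test against a justified external value. That is true in principle, so the conclusion here covers only comparisons within the trial. The documents give no such value.

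A third is that the Manual of Procedures (Appendix C) may define *natural bone fill*. It was not available, so the term can be called undefined only in the documents seen.

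Three stronger readings are tempting and are not supported:

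- **That the design is faulty without an ungrafted arm.** The stated purpose is allograft against amnion-enhanced allograft, and that purpose needs no such arm.
- **That the amnion comparison is compromised.** Step 2 of the working shows that it isolates a. Nothing here bears on its power.
- **That the sponsor plans to claim efficacy against ungrafted healing.** The sentences in the Rationale and 11.1 leave room for it, but no analysis of that kind is described, and the word relative in 11.1 points towards a between-group reading.

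**Conclusion.** The point holds within limits. Hypothesis-1 cannot be tested by any comparison inside this trial, because bone allograft is common to both arms and to every site within a participant. The defect is structural and its size is the count in step 1, so a larger sample would not change it. The planned CBCT and biopsy data can describe the Bone Allograft arm and no more.

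The conclusion rests on reading enhancement as improvement over healing without the graft, and on the absence of a benchmark from the documents seen. It concerns what may be said about bone allograft alone and leaves Hypothesis-2 untouched. The change should be made, but it corrects what the protocol promises rather than how the trial is run.

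**What to change.** In 2.3, delete Hypothesis-1 or replace it with a descriptive aim, for example: *Describe the percentage of new bone at week 8 in the Bone Allograft arm, from one biopsy per participant, with a 95% confidence interval. No claim of efficacy against ungrafted healing will be made.* Keep the amnion comparison as the tested hypothesis. If CBCT fill is also described, label it as total fill, not new bone.

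Align three other places:

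- in the synopsis Rationale, reword the promise about the efficacy of each application as a comparison between the two grafted arms;
- in 11.1, make the sentence on histology and new bone formation explicitly a comparison between those arms;
- in 13.1, say what *natural bone fill* means, or remove it if it refers to ungrafted sites.

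If the descriptive aim is kept, 13.4 needs one sentence for the confidence interval. The cost is protocol wording. The sponsor gives up only a conclusion that the design cannot support.

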13.4 Statistical Analysis Plan

Two-tailed t tests will be used to compare clinical characteristics between patients with the Bone Allograft (control therapy) and those with the Bone Allograft/Amnion Allograft (test therapy) for continuous variables with a normal distribution. Nonparametric (Wilcoxon) tests will be used otherwise.

For categorical variables, inter-group comparisons will be conducted using chi-square tests or Fisher's Exact Test, as deemed necessary. To determine whether the groups experienced equivalent changes in bone growth from baseline to follow-up, paired t (or Wilcoxon signed-rank) and McNemar's tests will be used for continuous and categorical variables, respectively.

The α level will be set at 0.05. Statistical analysis will be carried out using SAS software version 9.2 (SAS Institute, Inc, Cary, North Carolina).

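### The plan names no between-arm analysis that combines repeated visits, although Aims 3 and 8 and the healing-pattern null call for one

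*Combined protocol and SAP*

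**What the plan says.** **Questions that span visits.** The synopsis null is that "there is no difference in post-extraction healing patterns between extraction sockets grafted with Bone Allograft (BA) and extraction sockets grafted" with the combined material. In Section 2.3, Aim 3 is to "Compare soft tissue healing between groups at week-1, week-2, week-4 and after 7 weeks of post-extraction healing", which is four visits. Aim 8 is to "Assess changes in longitudinal crestal bone level between groups at 12 and 24 months after permanent prosthetic attachment", which is two. Aim 7 also spans two: "Compare implant stability between groups at 12 months and 24 months post-restoration". Section 13.3 adds that bone height at 12 and 24 months is compared with the value at insertion to derive changes, and that differences between groups will be used to judge osseous changes.

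**Methods.** Section 13.4, repeated in the synopsis, gives two-sided two-sample t tests for normally distributed continuous variables. For the rest, "Nonparametric (Wilcoxon) tests will be used otherwise". For categorical variables, "inter-group comparisons will be conducted using chi-square tests or Fisher's Exact Test, as deemed necessary". A further sentence, opening "To determine whether the groups experienced equivalent changes in bone growth from baseline to follow-up", assigns paired t, signed-rank and McNemar tests. Alpha is 0.05. No repeated-measures model, arm-by-visit term, summary over visits or multiplicity rule is named, and nothing says how the listed tests apply to an outcome recorded at several visits.

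**The concern.** A two-sample test takes one value per participant. A paired test links two time points, but within an arm, so it cannot say whether the arms changed by different amounts. Between them, the listed methods leave no analysis that brings a participant's follow-up visits together in a comparison of arms.

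Three things are at stake:

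- With 10 participants per arm, precision is scarce, and the repeated visits already scheduled are a cheap source of more.
- Tests at several visits can disagree, and the plan has no rule for reading a measure that is significant at week 2 but not at week 7.
- Because the plan is silent, the choice among a visit, a mean and a change score could be made after the data are seen.

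**Working it through.** **Inputs from the documents.** 20 participants, 10 per arm (Section 3.1); four visits for Aim 3 and two for Aim 8 (Section 2.3); alpha 0.05, two-sided t tests (Section 13.4). There is no stated power or sample-size figure to reproduce.

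**Assumptions, not in the documents.** One normally distributed value per participant per visit, SD 1, complete data, equal correlation r between visits of 0.3, 0.5, 0.7 or 0.9, and a steady arm difference of 1 SD.

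**1. Power at a single visit.** Noncentrality = d × √(n/2) = 1 × √5 = 2.236, with 18 degrees of freedom and critical value 2.101. Power is 56%.

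**2. Power of one test averaged over k visits.** The variance of a participant's mean is (1 + (k − 1)r)/k, so the standardised difference becomes 1/√[(1 + (k − 1)r)/k].

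| r | Four visits: variance | Difference | Power | Two visits: variance | Difference | Power |
|---|---|---|---|---|---|---|
| 0.3 | 0.475 | 1.45 | 87% | 0.65 | 1.24 | 75% |
| 0.5 | 0.625 | 1.26 | 76% | 0.75 | 1.15 | 69% |
| 0.7 | 0.775 | 1.14 | 67% | 0.85 | 1.08 | 63% |
| 0.9 | 0.925 | 1.04 | 60% | 0.95 | 1.03 | 58% |

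**3. False positives from visit-wise tests.** Four independent tests would give 1 − 0.95⁴ = 18.5%. Simulation of correlated visits gives about 18, 16, 13 and 10% at r = 0.3, 0.5, 0.7 and 0.9. For two visits the independent figure is 1 − 0.95² = 9.75%, and the correlated figures run from about 9.5% down to 7%.

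**4. Conflicting visits.** Under the steady 1 SD difference, about 72, 61 and 47% of simulated trials (r = 0.3, 0.5, 0.7) are significant at some of the four visits but not at others.

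**5. Where averaging loses.** Suppose the difference fades as 1, 1, 0.5, 0 SD. Its mean is 2.5/4 = 0.625. Dividing by the square roots of the four-visit variances gives 0.91, 0.79, 0.71 and 0.65, and power of about 48, 39, 32 and 28%. The best single visit still has 56%.

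**The case against.** Several stronger readings are tempting, and the documents do not support them.

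- *The plan prescribes visit-by-visit testing.* It does not say so. A t test on a participant's mean or change score would fit the wording of Section 13.4. Separate visit tests are the natural reading of Aim 3, but an inference.
- *Every between-arm comparison uses a single time point.* Section 13.3 derives crestal bone change from insertion, so each Aim 8 comparison uses two. What is missing is any joint use of the 12- and 24-month changes.
- *Repeated data are thrown away.* Visit-wise tests use every visit and answer Aim 3 as literally worded. With complete data and no covariates, a mixed model with free visit means gives the same arm difference at each visit. The loss lies in pooled contrasts, in missed visits and in resolving conflicts.
- *The main question of the trial has no analysis.* Healing patterns appear only in the synopsis null and are not defined. The hypotheses in Section 2.3 concern bone fill and ridge dimensions, which Aims 2, 4 and 5 take at week 7 alone.
- *The power gain shows what a pattern test would achieve.* A steady difference has no arm-by-visit interaction. The gain belongs to the averaged arm effect.

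Three practical objections stand and shape the remedy. The gain comes from averaging, not from the mixed model as such. Making both the average and the interaction tests at 5% would put the chance of at least one false positive near 10%, no better than two visit tests. Early soft-tissue healing is listed in Section 13.2 as subjective observation with no defined score, so a normal model may not suit it.

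**Conclusion.** The concern holds in limited form. Section 13.4 and the synopsis name no between-arm analysis combining repeated visits, and the tests assigned to the between-arm change question carry no arm contrast. That much follows from the text alone.

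The size rests on assumed effects and correlations. For a steady difference the gain from averaging is large at low correlation (56% to 87% over four visits at r = 0.3) and small at high correlation (56% to 60% at r = 0.9; 56% to 58% over two visits). An early effect that fades is diluted. A single pre-specified test also removes the inflation of roughly 10 to 18% for four visits and the problem of conflicting visits. This is an inexpensive improvement that should be made. It does not show that the planned comparisons are invalid.

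**What to change.** In Section 13.4 and the synopsis:

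1. For each continuous outcome recorded at more than one follow-up visit, pre-specify one repeated-measures mixed model on participant-level values (the mean over a participant's study sites). Include arm, visit, arm-by-visit, smoking stratum and the baseline value where one exists, with small-sample degrees of freedom. Include participants with whatever visits they have.
2. Name one test per aim at 0.05: the arm effect averaged over visits. Where an aim has several measures, say which one carries the test.
3. Report arm-by-visit as a secondary description of healing pattern. Report each visit's difference with a 95% confidence interval and no separate verdict.
4. For ordinal or clearly non-normal scores, apply the Wilcoxon test already named to the participant's mean over visits, and state how a missed visit enters that mean.
5. Replace the paired tests for the between-arm change question with this between-arm contrast.

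The cost is wording and a short program in the SAS package already named, with no new data, visits or participants. The price is dilution of an effect confined to early visits (28 to 48% power in the fading example, against 56% at the best visit). If an early effect is expected, the chosen contrast should say so before the data are seen.
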